monophosphate [cGMP]), tissue inhibitor of metalloproteinases 2 [TIMP-2], and insulin-like growth factor-binding protein 7 [IGFBP7] and organ protection. However, the effect of RIPC on AKI in patients with CAD undergoing cardiac catheterization is not well-established, and the underlying mechanism of such effect remains unclear.

2. Study Design and Objective

This is a prospective, double-blinded, two-center, randomized, sham-controlled clinical trial. The primary aim of this study is to determine whether remote ischemic preconditioning (RIPC) reduces the incidence of acute kidney injury (AKI) in high-risk patients undergoing coronary angiography and/or PCI. The secondary aim is to study the effect of RIPC on renal (TIMP-2 X IGFBP7) and vascular (cGMP) biomarkers, major adverse cardiac events (MACE), and major adverse kidney events (MAKE) during a 6-month follow-up period in high-risk patients undergoing coronary angiography.

3. Patient

Eligible male and female patients over the age of 18 years with unstable angina or non-ST elevation myocardial infarction (NSTEMI) who are at high risk for AKI and undergoing coronary angiography and/or PCI. The trial will be conducted at two tertiary hospitals in the United States, the University of Pittsburgh Medical Center and the affiliated Veterans Affairs Pittsburgh Healthcare System. AKI risk will be determined by a modified version of Mehran's risk score. The scoring system contains different risk factors, including patient characteristics, comorbidities and contrast volume. At the time of enrollment and prior to coronary angiography, the lowest range of contrast volume (1-100) in the scoring system will be utilized for calculation of modified Mehran risk score as shown in Table 1.³ After coronary angiogram, the actual volume of contrast used during the procedure will be utilized to calculate post-angiography Mehran risk score. A score of 11 or higher will be used to define patients at high risk for AKI as shown in Table 2.³ Patients with inability to provide informed consent, acute ST elevation myocardial infarction, unstable blood pressure (BP) (systolic BP > 200 or <90 mmHg), peripheral vascular disease, contrast allergy, renal disease requiring dialysis, or placement of arteriovenous fistula graft will be excluded.

Table 1: Scoring System for Predicting Acute Kidney Injury

Risk Factors	Score
Age > 75	4
Diabetes mellitus	3
NYHA Class III/IV Heart failure	5
Anemia (male: HCT<39, female: HCT<36)	3

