Hypotension (SBP<80mmHg or >1hr inotropic support)	5
Intra-aortic balloon pump placement	5
Estimated GFR < 20ml/min	6
Estimated GFR 20-40 ml/min	4
Estimated GFR 40-60ml/min	2
Contrast volume (1-100cc)	1
Contrast volume (101-200cc)	2
Contrast volume (201-300cc)	3
Contrast volume (301-400cc)	4
Contrast volume (401-500cc)	5

Table 2: Risk Score and Predicted Risk of Acute Kidney Injury and Dialysis

Mehran Risk Score	Risk of AKI	Risk of Dialysis
≤ 5	7.5%	0.04%
6-10	14%	0.12%
11-16	26.1%	1.09%
>16	57.3%	12.6%

Inclusion Criteria

- Adult patients over the age of 18 years
- Diagnosis of non-ST elevation myocardial infarction or unstable angina
- Referral for invasive coronary angiogram and/or percutaneous coronary intervention
- Acute kidney injury risk score of ≥ 11

Exclusion Criteria

- Inability to give informed consent
- Unstable blood pressure (systolic blood pressure > 200 or < 90 mmHg)
- History of allergy to contrast media
- Peripheral vascular disease of upper limb
- Renal disease requiring dialysis
- Placement of arteriovenous fistula and arteriovenous graft

4. Randomization and Blinding

A total of 110 patients will be randomized to the RIPC (55) treatment group or the Sham-RIPC (55) control group on a 1:1 basis. Randomization will be computer-generated using the REDCap data management application system. Unblinded statistician will set up a pre-defined allocation table with variable block sizes of 2 to 4, and stratification by site. Unblinded research staff will perform randomization and application of RIPC and sham-RIPC. Patients will be blinded by the use of Sham-RIPC in the control group. Investigators, cardiologist performing coronary angiography, clinical outcome assessors, and data analysts will be unaware of treatment assignment.

5. Procedures, blood and urine sampling and analysis

All patients will undergo coronary angiography and/or PCI using the standard technique. The decision to perform PCI, choice of guidewires, balloons, stent types, and characteristics will be made by the interventional cardiologist according to common laboratory practice and guideline for coronary angiography and interventions. All patients will receive standard medical therapy and hydration for coronary angiography and PCI. We will extract data on patient demographic and medical history including gender, age, race, comorbidities, and coronary angiography

findings from the electronic medical record.

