After randomization, we will perform RIPC or Sham-RIPC approximately 1-4hrs before coronary angiography. The patients assigned to RIPC will undergo 3 cycles of 5-minute inflation of a standard blood-pressure cuff to 200 mmHg, followed by 5-minute cuff deflation. In patients assigned to the control group, sham-RIPC will be induced using 3 cycles of 5-minute blood pressure cuff inflation to a pressure of 10 mmHg, followed by 5-minute cuff deflation.

For the primary aim outcome of AKI, blood samples will be drawn at baseline and then at 24hrs and 48hrs after coronary angiography for measurement of serum creatinine using the standard laboratory protocol. Urinary insulin-like growth factor-binding protein 7 (IGFBP7) and tissue inhibitor of metalloproteinases 2 (TIMP-2), both inducers of G1 cell cycle arrest, are implicated in AKI and serve as biomarkers to predict it.⁴ The product of urinary TIMP-2 and IGFBP7 concentrations, (TIMP-2) \times (IGFBP7), will be measured with the NephroCheck Test. We will measure urinary TIMP-2 \times IGFBP7 from samples obtained at baseline, immediately after three cycles of RIPC but before coronary angiography, 24hrs, and 48hrs after coronary angiography. These assays will be performed at the Center for Critical Care Nephrology core laboratory at the University of Pittsburgh according to the standard manufacturer's specification. Plasma concentration of cyclic guanylate monophosphate (cGMP) will be measured using blood samples obtained at baseline, immediately after 3 cycles of RIPC but before coronary angiography, 24hrs, and 48hrs after coronary angiography. These assays will be performed at the Center for Microvascular Research laboratory at the University of Pittsburgh using the standard enzyme immunoassay kit.

6. Outcomes

The primary end point is the occurrence of AKI, defined as a relative increase in serum creatinine of $\geq 0.3\text{mg/dl}$ compared with baseline creatinine within 48 hours after coronary angiography according to the Kidney Disease: Improving Global Outcomes guideline.⁵ Secondary biomarker endpoints include the product of urinary concentrations of TIMP-2 and IGFBP7 and plasma concentration of cGMP. Other secondary clinical outcomes are 1) major adverse cardiovascular and

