Secondary outcomes (biomarkers): the goal is to characterize changes in the product of TIMP2 and IGFBP7 and plasma cGMP following RIPC in patients with CAD undergoing coronary angiogram. We will test the association of RIPC with levels of each molecule (RIPC vs. non-RIPC groups) using parametric statistics (t-test, confidence intervals for differences) when levels were normally distributed (expected), or using transformed levels if not. If distributions are very unbalanced, nonparametric tests will be used. The extent of protocol violations and missing outcome data will be quantified overall and by random assignment. All statistical analyses will be performed using SPSS.

8. *Ethics*

The written informed consent form, and overall study protocol and materials will be reviewed and approved by the IRB before the initiation of this trial. A Data and Safety Monitoring Board (DSMB) will be created to review this study. The DSMB will meet after initial approval with plan for quarterly meeting. However, the follow-up meeting frequency of the DSMB will be determined during the first meeting. An emergency meeting of the DSMB will be called at any time by the Chairperson should questions of patient safety arise.

9. *Informed consent*

All study patients will be provided with an easily understandable informed consent form approved by the IRB. The patients will be enrolled after signing the informed consent form. The informed consent form will be kept as an important document of the clinical trials for future reference.

References

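### Biomarker analysis aims at changes but tests levels between arms, and the collected baseline sample has no stated role, which gives up precision

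*Combined protocol and SAP*

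**What the plan says.** Section 2 makes the biomarkers part of the secondary aim: "The secondary aim is to study the effect of RIPC on renal (TIMP-2 X IGFBP7) and vascular (cGMP) biomarkers".

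Section 5 schedules the urinary marker "from samples obtained at baseline, immediately after three cycles of RIPC but before coronary angiography, 24hrs, and 48hrs after coronary angiography". It gives cGMP the same four times: "Plasma concentration of cyclic guanylate monophosphate (cGMP) will be measured using blood samples obtained at baseline", then after the conditioning cycles, at 24 hours and at 48 hours.

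Section 6 lists the biomarker endpoints only as a product and a concentration, with no time point and no definition of change.

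In section 7, under Secondary outcomes (biomarkers), "the goal is to characterize changes in the product of TIMP2 and IGFBP7 and plasma cGMP following RIPC". The method follows: "We will test the association of RIPC with levels of each molecule (RIPC vs. non-RIPC groups) using parametric statistics", namely "t-test, confidence intervals for differences) when levels were normally distributed (expected), or using transformed levels if not". The fallback is: "If distributions are very unbalanced, nonparametric tests will be used".

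The only use of baseline variables in section 7 is the logistic regression, which concerns AKI. Section 4 specifies "variable block sizes of 2 to 4, and stratification by site", but site does not appear in the biomarker analysis.

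**The concern.** The goal and the test name different quantities. An analyst could follow the text with a t-test on post-baseline levels or with a t-test on change from baseline, at any of three later times. These are different analyses and can disagree on the same data. Neither is generally as precise as a comparison that uses the baseline value as a covariate, and the transformed and nonparametric fallbacks bring in no baseline value either.

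The trial's mechanistic question is at stake. It rests on these two markers, with about 50 evaluable patients per arm, a number chosen for AKI alone. The baseline assays are already planned, so the information is available and unused.

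**Working it through.** **The plan's own power figure.** Section 7 states 88% power for AKI at 35% versus 10% with 50 per arm. Using the unpooled normal formula and two-sided 5% (assumed, since the plan states no level):

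0.25 / √[(0.35×0.65 + 0.10×0.90)/50] = 0.25/0.0797 = 3.14; 3.14 − 1.96 = 1.18; power 88.0%.

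The figure reproduces (86.1% with pooled variance), but it concerns AKI only. The plan gives no SD, effect size or power for the biomarkers.

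**Inputs for the biomarkers.**
- From section 7: 50 evaluable patients per arm.
- Assumed: a true difference of 0.5 SD, a two-sided 5% test, equal SD at baseline and follow-up, and a baseline-to-follow-up correlation r of 0.3, 0.5 or 0.7.

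**Variance of the arm difference, relative to a t-test on levels.**
- Levels: 1
- Change from baseline: 2(1 − r)
- ANCOVA on baseline: 1 − r²

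**Power.** The noncentrality is 0.5 × √(50/2) / √(relative variance) = 2.5 / √(relative variance). Power comes from the noncentral t distribution with 98 degrees of freedom (97 for ANCOVA).

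| | r = 0.3 | r = 0.5 | r = 0.7 |
|---|---|---|---|
| Levels t-test | 69.7% | 69.7% | 69.7% |
| Change-score t-test | 55.3% | 69.7% | 89.2% |
| ANCOVA | 73.7% | 81.5% | 93.4% |
| Cut in standard error, ANCOVA vs levels: 1 − √(1 − r²) | 4.6% | 13.4% | 28.6% |
| Patients per arm a levels test needs to match: 50/(1 − r²) | 55 | 67 | 98 |
| Difference detectable at 80% power, ANCOVA (levels: 0.57 SD) | 0.54 SD | 0.49 SD | 0.40 SD |

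A simulation of 40,000 trials gave ANCOVA power of 72.9%, 80.8% and 93.1%. The levels and ANCOVA estimates both averaged 0.50 SD, so both are unbiased.

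**Do the two readings matter?** In 20,000 simulated trials under the same assumptions, the levels and change-score t-tests disagreed on significance in 31%, 29% and 29% of trials at r = 0.3, 0.5 and 0.7.

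**Unnamed time point (supporting).** Two markers at three later times make six possible tests. If all were run at 5% with independent results, the chance of at least one false positive would be 1 − 0.95⁶ = 26.5%. With independent markers and a between-time correlation of 0.9 it would be 16.0%. Two named tests give 1 − 0.95² = 9.75%.

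**The case against.** The strongest reply is that a t-test between randomized arms is valid, the markers are secondary, no power is claimed for them, and the size of any gain rests on a correlation the documents do not give. Four parts of this stand.

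- **Low correlation.** At r = 0.1 ANCOVA has 70.1% power by the formula, and 69.7% once the cost of estimating the slope is counted (variance factor 1 + 1/96). That is no gain over levels. At r = 0.2 it has 71.4%, or 71.0% with that cost. A low r is possible at 24 and 48 hours, because contrast is given after the baseline sample.
- **Equal variance.** The change-score figures depend on it. If the follow-up SD were 1.5 times the baseline SD, the relative variance of change would be 1 + 1/1.5² − 2r/1.5, and change-score power would be 67.8%, 80.1% or 93.4%. That is within about 6, 1 and 0 points of ANCOVA.
- **The stated goal can be read as pointing to change scores.** On that reading baseline enters by subtraction. The text never says so, and the sentence that names the test refers to levels.
- **Multiplicity is conditional.** The plan does not say that six tests will each be declared significant.

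The plan's transformation and nonparametric provisions and its blinded data analysts are sound and not in dispute. Blinding limits selective choice of analysis, but it does not state which analysis is planned. None of these points gives the baseline sample a role or removes the mismatch between goal and test. At low correlation, adjustment costs almost nothing.

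**Conclusion.** The concern holds. The stated goal and the stated test differ, no section assigns the baseline biomarker value a role, and no main time point is named.

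The consequence is lost precision and an ambiguous secondary analysis, not bias. Relative to a levels t-test, ANCOVA would add about 4, 12 or 24 points of power at correlations of 0.3, 0.5 or 0.7, and close to none at 0.1. These gains assume 50 per arm, a 0.5 SD difference and a two-sided 5% test. The change-score comparison also assumes equal variance at both times. The change should be made because it uses data already collected at almost no cost. The primary AKI analysis, sample size and safety are not affected.

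**What to change.** In section 7, replace the biomarker t-test with one of the following for each marker:

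- ANCOVA at each post-baseline time, with arm, baseline value and site; or
- one linear mixed model on the post-baseline values, with arm, time, arm-by-time, baseline value, baseline-by-time and site.

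Site belongs in the model because it is the randomization stratum. Use the log scale where values are skewed, as the transformation provision already allows, and a rank-based ANCOVA where a nonparametric test would have been used. Report the arm contrast at each time with its confidence interval. As a supporting step, name one main time per marker before unblinding and label the other times supportive.

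The cost is a few sentences of wording and slightly more analysis work, all possible in SPSS, with no new patients or samples. There are three downsides. Log-scale effects are reported as geometric mean ratios. Patients without a baseline sample need a stated handling rule. Two main tests, one per marker, still carry a family error of about 10%.

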Clinical Trial Protocol
Biochemical and Reno-Protective Effects of Remote Ischemic Preconditioning on
Contrast-Induced Kidney Disease (BRICK) Trial

Version	Date	Main reason for changes
1	12/20/2017	Not applicable
2	02/26/2019	Addition of a second trial site

1. *Background*

Acute kidney injury (AKI) is a common complication of intravenous, iodinated contrast media, that is widely used for cardiac catheterization and percutaneous coronary intervention (PCI) in patients with coronary artery disease (CAD).^{1,2} In the United States, CAD remains the number one cause of death in both men and women despite improvement in the care of patients over the last decade. Although PCI restores blood flow to the heart, the contrast media used for the procedure can cause AKI, possibly mediated by contrast-induced vasoconstriction of renal blood vessels and free radical-mediated direct renal tubular toxicity. The incidence of AKI is estimated to range between 10 and 40% in patients undergoing cardiac catheterization with higher rates in patients with acute myocardial infarction.^{1,2} In the United States, approximately 1.4 million cardiac catheterization procedures are performed each year, and this estimate is expected to increase exponentially in the next few decades. With increasing use of contrast media, the prevalence of AKI is also expected to rise. AKI predicts elevated risk of heart attack, longer in-hospital stay, more complicated hospitalization course, and higher in-hospital mortality. Unfortunately, there is no effective prophylactic regimen to prevent AKI.

Remote ischemic pre-conditioning (RIPC), elicited by application of one or more brief episodes of ischemia and reperfusion of a limb, is a promising therapy for preventing or attenuating AKI. Given that renal ischemic injury and tubular toxicity are the most common pathophysiological concepts of AKI, it stands to reason that RIPC may prevent AKI via nitrite-induced vasodilation and damage associated molecular protein -mediated renal cell protection. Our preliminary data suggest that RIPC provides renal protection and indicate a connection between RIPC-induced changes in protective molecules (nitrite, cyclic guanosine

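### The biomarker analysis fixes no lead time point, favourable direction, multiplicity rule or use of baseline for two markers that are each sampled three times after the cuff

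*Combined protocol and SAP*

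**What the plan says.** Section 6 (Outcomes) sets two biomarker endpoints: "Secondary biomarker endpoints include the product of urinary concentrations of TIMP-2 and IGFBP7 and plasma concentration of cGMP". Section 5 (Procedures) gives the sampling. The urinary product is measured in "samples obtained at baseline, immediately after three cycles of RIPC but before coronary angiography, 24hrs, and 48hrs after coronary angiography", and cGMP in "blood samples obtained at baseline, immediately after 3 cycles of RIPC but before coronary angiography, 24hrs, and 48hrs after coronary angiography". Each marker therefore has one baseline value and three values after the cuff.

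Section 7 (Statistical analysis, secondary outcomes) states that "the goal is to characterize changes in the product of TIMP2 and IGFBP7 and plasma cGMP following RIPC". The test follows: "We will test the association of RIPC with levels of each molecule (RIPC vs. non-RIPC groups) using parametric statistics". It is a t-test with confidence intervals for differences, on transformed values if the distribution is not normal, or nonparametric if distributions look badly unbalanced. Neither the transformation nor the threshold for going nonparametric is defined. Section 7 gives no time point, expected direction, multiplicity rule, baseline adjustment or longitudinal model for these endpoints.

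On direction, Section 1 (Background) says that preliminary data "indicate a connection between RIPC-induced changes in protective molecules" and then, in the same sentence, adds TIMP-2 and "insulin-like growth factor-binding protein 7 [IGFBP7] and organ protection". Section 5 describes TIMP-2 and IGFBP7 as "implicated in AKI and serve as biomarkers to predict it". For the primary outcome, by contrast, Section 7 states that a reduction in AKI is expected.

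**The concern.** A t-test needs one value per patient, and here there are three after the cuff, plus a baseline. The analyst must either pick one time or test several, and must choose between levels and changes from baseline. The plan settles neither question, so the choice can be made after the data are seen.

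Direction matters most at the sample taken after the cuff and before contrast. A higher TIMP-2 x IGFBP7 product in the RIPC arm at that moment could be reported as an induced protective response (Background) or as kidney stress (Section 5).

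At stake is the credibility of the mechanistic part of the secondary aim. A single nominally significant result among several possible ones would be hard to interpret if nothing shows that it was the contrast intended.

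**Working it through.** **Inputs from the documents.** Two markers; three post-cuff times each; 50 analysed patients per arm (Section 7). 

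**Inputs assumed.** Two-sided 5% per test, since no significance level is stated for any endpoint; the two markers independent of each other; equal correlation between any two times within a marker, varied from 0 to 0.9.

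**The plan's own figure.** No power or error rate is given for the biomarkers. The only stated power is for AKI: 88% for 35% versus 10% with 50 per arm. It helps to infer the significance level:

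- Unpooled variance, two-sided 5%: 0.25 / √(0.35×0.65/50 + 0.10×0.90/50) = 0.25 / 0.0797 = 3.137; 3.137 − 1.960 = 1.177, which gives 88.0%.
- Pooled variance, two-sided 5%: 86.1%.
- Pooled variance, one-sided 5%: 92.1%, which does not fit.

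A two-sided 5% level is thus a reasonable assumption for the biomarkers too, but it remains an assumption.

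**Number of basic contrasts.** 2 markers × 3 times = 6. This is a ceiling on the basic contrasts, because the plan does not say that each time is tested. The open choices of level or change, and of raw, transformed or nonparametric analysis, could add further analyses.

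**Chance of at least one false positive over six tests.** With independent tests:

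- Any difference, either direction: 1 − 0.95^6 = 26.5%.
- One pre-stated direction per contrast (2.5% in the favourable tail): 1 − 0.975^6 = 14.1%.
- The protocol's wording applied contrast by contrast: cGMP is called protective, so only a rise supports RIPC (three contrasts at 2.5%). TIMP-2 x IGFBP7 predicts AKI, so after contrast only a lower value supports RIPC (two contrasts at 2.5%). Before contrast either direction could be argued (one contrast at 5%). This gives 1 − 0.975^5 × 0.95 = 16.3%.

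With correlated times, by simulation (1,000,000 draws per setting):

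| Assumed within-marker correlation | Any difference | Supportive on the protocol's wording | One stated direction throughout |
|---|---|---|---|
| 0 | 26.5% | 16% | 14.1% |
| 0.5 | 23.4% | 15% | 12.1% |
| 0.7 | 20.6% | 13% | 10.6% |
| 0.9 | 16.1% | 11% | 8.3% |

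**With one lead contrast per marker.** Two unadjusted tests: 1 − 0.95² = 9.75%. With Holm over the two: at most 5%. The improvement therefore has two parts, fewer tests and the adjustment.

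**Price of the adjustment.** The difference detectable with 80% power at 50 per arm is (1.960 + 0.842) × √(2/50) = 0.56 SD at the 5% level and (2.241 + 0.842) × √(2/50) = 0.62 SD at 2.5%, the level of Holm's first step.

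**The case against.** These are secondary, mechanistic endpoints. The stated goal is to characterise, confidence intervals are already promised, and many trials report such markers without multiplicity control. That much is fair: whether to use Holm, and which times lead, is partly the sponsor's choice. Holm over all six contrasts would also hold 5% without naming a lead, at a first-step level of 0.05/6 = 0.0083. But Section 7 also says the association will be tested, Section 6 lists the markers as secondary endpoints, and nothing labels them exploratory.

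Four stronger readings are tempting, and the documents do not support them.

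- A reader might infer that the biomarker aim cannot fail. Under no effect, 74% to 84% of trials would show no significant difference on any of the six contrasts (100% minus 26% to 16%).
- A reader might infer that almost any difference could be claimed as support. The wording closes one direction for five of the six contrasts; only pre-contrast TIMP-2 x IGFBP7 is open both ways. The 16% to 26% range counts differences in either direction, so it overstates false support.
- A reader might infer that the Background and Section 5 contradict each other. The bracket after the protective molecules closes at cGMP, so that label is not strictly applied to TIMP-2 or IGFBP7. A fall in a predictor of AKI is also a change that fits with organ protection. The direction is unstated, not contradictory.
- A reader might infer that each time will be tested on a different set of patients. That follows only if times are tested separately with samples missing, and Section 7 does not say they will be.

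**Conclusion.** The point holds as a gap in specification. The plan fixes neither the lead time, the favourable direction, the multiplicity rule nor the use of baseline for either marker, and it leaves the scale of analysis to be chosen from the data. If all six contrasts are tested, the chance of at least one false-positive difference is about 16% to 26%, and of a falsely supportive one about 11% to 16%. Both ranges rest on an assumed two-sided 5%, independent markers, and within-marker correlations of 0.9 to 0, none of which the documents give. The implied direction for five contrasts is read from the Background and Section 5; it is not a stated hypothesis. The primary AKI comparison is not touched. This is worth correcting because it is cheap, not because it threatens the trial's main conclusion.

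**What to change.** Amend the biomarker paragraph of Section 7 before unblinding.

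1. Name one lead contrast and its favourable direction per marker. For example: TIMP-2 x IGFBP7 at 24 hours after angiography, lower with RIPC; cGMP immediately after the cuff, higher with RIPC. The sponsor may prefer other times; what matters is that they are named in advance.
2. State how a rise in TIMP-2 x IGFBP7 before contrast will be read.
3. Estimate all three post-cuff times from one repeated-measures model per marker, adjusted for the baseline value, on a transformation fixed in advance. This uses the baseline sample, serves the stated interest in changes, and lets patients with a missing sample still contribute.
4. Test the two lead contrasts two-sided with Holm, and state the significance level.
5. Report the other four contrasts descriptively with 95% confidence intervals.

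The cost is wording only: no further patients, samples or assays. The downside is that those four contrasts are no longer confirmatory, and that Holm's first step raises the detectable difference from about 0.56 to 0.62 SD, before any gain from baseline adjustment.
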